## 10. Study Population

The study population will include subjects with vision loss from LHON due to the G11778A point mutation in the mitochondrial *ND4* gene. Subjects with vision loss of up to 1 year in duration will be included.

### 10.1 Number of Subjects

Details of the estimations for the sample size calculation are provided in Section 16. Briefly, considering the study design with two treatment arms and a Standard Deviation (SD) of 0.50 for the change from baseline of the LogMAR visual acuity in *ND4* LHON subjects, to show a clinically significant difference of 0.3 LogMAR (equivalent to 15 ETDRS letters) with a study power of 80%, approximately 45 treated and evaluable subjects are needed per treatment arm and approximately 90 treated and evaluable subjects are needed for the study in total.

It is estimated that the screen failure rate for the intended study population will be approximately 23%. Therefore, to reach approximately 90 treated and evaluable subjects for the study, approximately 117 subjects will be screened.

Subjects who do not meet selection and non-selection criteria may be re-screened under Sponsor approval.

It is expected that the rate of dropout from the study prior to the primary timepoint (i.e. Year 1.5) will be low, estimated to be less than 5%. Depending on the number of subjects who terminate early, additional subjects may be enrolled through the end of the recruitment period.

### 10.2 Selection for the Study

#### 10.2.1 Selection Criteria

Subjects must meet all the following criteria at Screening Visit (Visit 1) to be eligible for inclusion.

1. Age 15 years or older on the date of signed informed consent.
2. Clinically manifested vision loss due to *ND4* LHON, to any extent, in at least one eye.
3. Vision loss duration of  $\leq 365$  days (i.e.  $\leq 1$  year) in each affected eye at Inclusion Visit (Visit 2).
4. Female subjects (if of childbearing potential) must agree to use effective methods of birth control for up to 6 months after Treatment Visit(s) 3 and male subjects must agree to use condoms for up to 6 months after Treatment Visit(s) 3.
5. Ability to obtain adequate pupillary dilation to permit thorough ocular examination and visual testing.
6. Subject – and parent/legal guardian if the subject is under 18 years of age – has provided signed, written informed consent.

#### 10.2.2 Non-Selection Criteria

Subjects meeting any of the following criteria at Screening Visit 1 will be excluded from eligibility.

1. Any known allergy or hypersensitivity to GS010 or its constituents.

2. Contraindication to intravitreal injection in any eye.
3. Intravitreal drug delivery to any eye within 30 days prior to the Screening Visit (Visit 1).
4. Previous vitrectomy in either eye.
5. Narrow angle in any eye contra-indicating pupillary dilation.
6. Presence of disorders or diseases of the eye or adnexa, excluding LHON, which may interfere with visual or ocular assessments, including SD-OCT, during the study period.
7. Presence of known/documented mutations, other than the G11778A *ND4* LHON-causing mutation, which are known to cause pathology of the optic nerve, retina or afferent visual system.
8. Presence of systemic or ocular/vision diseases, disorders or pathologies, other than LHON, known to cause or be associated with vision loss, or whose associated treatment(s) or therapy(ies) is/are known to cause or be associated with vision loss.
9. Presence of optic neuropathy from any cause except LHON.
10. Presence of illness or disease that, in the opinion of the Investigator, include symptoms and/or the associated treatments that can alter visual function, for instance cancers or pathology of the central nervous system, including Multiple Sclerosis (diagnosis of Multiple Sclerosis must be based on the 2010 Revisions to the McDonald Criteria [Polman 2011]).
11. History of recurrent uveitis (idiopathic or immune-related) or active ocular inflammation.
12. Participation in another clinical trial and receiving an IMP within 90 days prior to the Screening Visit (Visit 1). Exception: subjects remain eligible if they completed a clinical trial with idebenone as an IMP less than 90 days prior to Visit 1 AND completely discontinued idebenone at least 7 days prior to Visit 2.
13. Previous treatment with ocular gene therapy in either eye.
14. Subjects refusing to discontinue idebenone.
15. Subjects who have undergone ocular surgery of clinical relevance (per Investigator assessment) within 90 days preceding the Screening Visit (Visit 1).
16. Female Subjects who are, or who intend to breast feed during the initial six months' post-administration of GS010.
17. Subjects who unable to tolerate (e.g. the immune modulating regimen) or unable or unwilling to comply with all the protocol requirements.

### 10.2.3 Inclusion Criteria

Subjects must meet all the following criteria at Inclusion Visit (Visit 2) to be eligible for inclusion.

1. Vision loss duration of  $\leq 365$  days (i.e.  $\leq 1$  year) in each affected eye at Inclusion Visit (Visit 2).
2. Each eye of the subject must maintain at least Hand Motion (HM) visual acuity, as defined by the study's SOP for visual acuity testing.
3. Documented results of genotyping showing the presence of the G11778A mutation in the *ND4* gene and the absence of the other primary LHON-associated mutations (*ND1* or *ND6*) in the subject's mitochondrial DNA.
4. Have a negative test for infection with human immunodeficiency virus (HIV).

5. Female subjects of childbearing potential must have a negative pregnancy test for (a woman who is two years post-menopausal or surgically sterile is not considered to be of childbearing potential).
6. Review of all selection criteria to ensure continued compliance.

#### 10.2.4 Exclusion Criteria

Subjects meeting any of the following criteria at Inclusion Visit 2 will be excluded from eligibility.

1. Light Perception (LP) or No Light Perception (NLP) visual acuity in any eye, as defined by the study's standard operating procedure (SOP) for visual acuity testing.
2. Subjects taking idebenone who have not completely discontinued the idebenone at least 7 days prior to Visit 2. If the subject has not discontinued idebenone at least 7 days prior to Visit 2, Visit 2 may be delayed until the 7-day period is complete as long as the study visit windows are adhered to.
3. Presence of active infectious conjunctivitis, keratitis, scleritis or endophthalmitis in either eye.
4. Presence of alcoholism, alcohol dependence, or alcohol or drug abuse (excluding nicotine).
5. Presence of systemic illness or medically significant abnormal laboratory values that are deemed by the Investigator to preclude the subject's safe participation in the study.
6. Any medical or psychological condition that, in the opinion of the Investigator, may lead to non-tolerance of the treatment regimen, may compromise the safe participation of the subject in the study or would preclude compliance with the study protocol or ability of the subject to successfully complete the study.
7. Any non-selection criteria which may have appeared after the screening visit.

#### 10.2.5 Deviation from Criteria for Selection

No protocol deviation related to study inclusion or exclusion criteria, conduct of the trial, subject management, or subject assessment will be allowed prospectively.

## 11. Study Conduct

Note: Study Day 0 is the day that treatment administration is completed to both eyes; in the setting of treatment administration on consecutive days, this will be the second treatment day. All timing of visits and visit windows are in reference to this Study Day 0.

### 11.1 Study Procedures by Visit

#### 11.1.1 Screening Visit (Visit 1)

Screening Visit 1 will be conducted from 28 to 7 days prior to Study Day 0. The following procedures will be performed at Visit 1:

- Informed consent of First Period read, understood, and signed by the subject. If the subject is unable to read the informed consent document, presence of an impartial witness is required to confirm that the contents of the document were explained to the subject. The impartial witness must sign the informed consent form (ICF). The subject must always be asked to sign or mark the ICF regardless of their visual ability. If the subject is under the legal age of consent, the potential subject's parent or legal guardian will be given an ICF for review, and the minor subject will sign a pediatric assent form, according to applicable local regulation.
- Assess subject's eligibility for the study with the selection and non-selection criteria. If the subject fails to comply with any of these criteria, the subject will not be selected for study participation and no further assessments will be conducted.
- Collection of subject demographic information, including gender, date of birth and age, tobacco use (e.g. cigarette smoking) and alcohol consumption, relevant medical and surgical history, including history related to symptoms and diagnosis of LHON, and prior relevant medications.
- Documentation of vision loss duration for each eye and determination of the first affected eye and the second affected/not yet affected eye.
- Assessment of physical examination, including general appearance, skin, head, eyes, ears, nose, throat, neck, thyroid, chest/lungs, heart, abdomen, lymph nodes, extremities, height, and body weight.
- Assessment of vital signs including blood pressure (BP), pulse rate, and temperature.
- 12-lead ECG.
- Blood draw for genotyping to confirm the presence of the G11778A mutation in the mitochondrial *ND4* gene. All subjects are required to have a blood sample for genotyping sent to the study's central laboratory. Eligibility for selection/inclusion may be determined with a prior, reliable genotyping result obtained at a non-study laboratory, confirming the G11778A *ND4* mitochondrial mutation and the absence of the *ND1* and *ND6* mitochondrial mutations.
- Blood draws for hematology, serum chemistries, HIV testing and pregnancy testing for female subjects of childbearing potential. All subjects are required to have blood samples for hematology, serum chemistries, HIV testing and serum pregnancy test (for female subjects of childbearing potential) sent to the study's central laboratory. Eligibility for

selection/inclusion may be determined with recently performed, reliable test results obtained at a local, non-study laboratory.

- Blood draw for humoral immune response to AAV2, obtained prior to initiation of the immune modulating regimen.
- Blood draw for cellular immune response to AAV2, obtained prior to initiation of the immune modulating regimen.
- Blood draw for bio-dissemination, obtained prior to initiation of the immune modulating regimen.
- Refraction for BCVA, performed prior to pupil dilation.
- Visual acuity assessment performed prior to pupil dilation.
- Pelli-Robson contrast sensitivity test performed prior to pupil dilation.
- HVF 30-2, performed prior to pupil dilation.
- Goldmann applanation tonometry for IOP measurement, performed prior to pupil dilation.
- Slit lamp examination (SLE) performed pre- and post-pupil dilation.
- SD-OCT, performed after pupil dilation.
- Recording of any AE or SAE.
- Recording of any concomitant medications and supplements.
- The immune modulating regimen will be initiated after conducting the Screening Visit (Visit 1) and prior to conducting the Inclusion Visit (Visit 2).

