#### 11.1.2 Inclusion Visit (Visit 2)

Inclusion Visit (Visit 2) will be conducted 2 days prior to Study Day 0, or 1 day prior to Study Day 0, as determined by the treatment administration option selected. The following procedures will be performed at Visit 2:

- Assess subject's eligibility for to the study with the inclusion and exclusion criteria. If the subject fails to comply with any of these criteria, the subject will be excluded from the study and no further assessments will be conducted.
- Record the occurrence of new onset vision loss occurring since Visit 1 in eyes previously unaffected by clinically manifested vision loss with documentation of the date of onset of vision loss and the vision loss duration.
- Determination and documentation of the best-seeing and worst-seeing eye of the subject.
- Review of laboratory assessment results obtained at Visit 1 to confirm subject's eligibility for inclusion.
- Highly sensitive urine pregnancy test obtained only if applicable per local regulatory requirement.
- Assessment of VFQ-25 QoL scale. This must be performed prior to any vision or ocular assessments.
- Assessment of SF-36v2 QoL scale. This must be performed prior to any vision or ocular assessments.
- Refraction for BCVA, performed prior to pupil dilation.
- Visual acuity assessment performed prior to pupil dilation.
- Pelli-Robson contrast sensitivity test performed prior to pupil dilation.

- HVF 30-2, performed prior to pupil dilation.
- Goldmann applanation tonometry for IOP measurement, performed prior to pupil dilation.
- SLE, performed pre- and post-pupil dilation.
- SD-OCT performed after pupil dilation.
- Color fundus photo performed after pupil dilation.
- Recording any AE or SAE.
- Recording of any changes and additions to concomitant medications and any changes in concomitant medication dose or regimen, including supplements.

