#### 11.1.3 Treatment Visit (Visit 3)

Treatment Visit(s) 3 may be conducted in one day or in two consecutive days (i.e. Study Day 0, or day -1 and Study Day 0). The initial treatment administration must be conducted the day following the Inclusion Visit (Visit 2). When both eyes are treated the same day, treatment must be performed the day after Inclusion Visit (Visit 2). The following procedures will be performed at the treatment administration visit(s):

- Assessment of vital signs including BP, pulse rate, and temperature, per the Intravitreal GS010/Placebo Injection Guide.
- Goldmann applanation tonometry for IOP measurement, per the Intravitreal GS010/Placebo Injection Guide.
- SLE, performed pre- and post-pupil dilation per the Intravitreal GS010/Placebo Injection Guide.
- Administration of GS010 and/or placebo via intravitreal injection, according to the randomized treatment allocation, per the Intravitreal GS010/Placebo Injection Guide.
- Recording of any changes and additions to concomitant medications and any changes in concomitant medication dose or regimen, including supplements, pre- and post-IMP/placebo administration.
- Recording any AE or SAE that has occurred, pre- and post-IMP/placebo administration.

#### 11.1.4 Post-Treatment Follow-Up Period 1 and Period 2: Visits 4 through 16

Follow-up visits (Visits 4 through Visit 16) will be conducted post-treatment administration. During the Post-Treatment Follow-Up Period 1, ten follow-up visits, Visits 4 through 13 with 2 optional telephone visits, then in the Post-Treatment Follow-Up Period 2, 3 additional follow-up visits, Visit 14 through 16, are scheduled to be conducted at the following time points and with the following assessments:

##### 11.1.4.1 Visit 4 – Day 1

Visit 4 will be conducted one day after Study Day 0, i.e. one day after completion of the treatment administration to both eyes of a subject. The following procedures will be conducted at Visit 4:

- Assessment of vital signs including BP, pulse rate, and temperature.
- Refraction for BCVA, performed prior to pupil dilation.
- Visual acuity assessment performed prior to pupil dilation.

- Pelli-Robson contrast sensitivity test performed prior to pupil dilation.
- HVF 30-2, performed prior to pupil dilation.
- Goldmann applanation tonometry for IOP measurement, performed prior to pupil dilation.
- SLE, performed pre- and post-pupil dilation.
- SD-OCT performed after pupil dilation.

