### 12.3 Laboratory Evaluations

#### 12.3.1 ND4 (G11778A) Genotyping

All subjects are required to have a blood sample for *ND4* genotyping sent to the study's central laboratory at Screening Visit 1. Eligibility for selection/inclusion may be determined with a prior reliable genotyping result obtained at a non-study laboratory confirming the G11778A *ND4* mitochondrial mutation and the absence of the *ND1* and *ND6* mitochondrial LHON point mutations. The presence of the G11778A *ND4* mitochondrial DNA mutation must be documented by the completion of Inclusion Visit 2 and prior to randomization.

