#### 12.3.2 Hematology and Serum Chemistries

Blood samples will be collected for the following hematology and serum chemistries tests during the study per the study schedule:

- Hematology tests: Complete blood count including red blood cells, hemoglobin, hematocrit, white blood cells with differential, and platelets.
- Serum chemistry tests: Glucose, lipase, amylase, calcium, sodium, potassium, chloride, bicarbonate, blood urea nitrogen (BUN) and creatinine and the Liver Function Tests: AST (aspartate aminotransferase), ALT (alanine aminotransferase), ALP (alkaline phosphatase),  $\gamma$ GT (Gamma-glutamyl transpeptidase), total bilirubin, and albumin.

All subjects are required to provide a blood sample at Screening Visit 1 for hematology and serum chemistries. Eligibility for inclusion may be determined with recently performed, reliable, hematology and serum chemistries obtained at a local, non-study laboratory or reliable hematology and serum chemistries to be obtained at a local non-study laboratory. In all cases (i.e. use of local or central laboratory results for determination of inclusion eligibility) results must be available by Inclusion Visit 2 to be considered for eligibility for inclusion. At all subsequent visits hematology and serum chemistries will be performed only at the study's central laboratory only.

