#### 12.3.3 HIV Testing

Blood samples for HIV testing may be obtained for analysis in the study's central lab at the Screening Visit 1. However, eligibility for inclusion may be determined with a recently performed, reliable, HIV test obtained at a local, non-study laboratory, or a reliable HIV test to be obtained at

a local, non-study laboratory. In all cases the results of the HIV test must be available and documented by Visit 2. Subjects with positive tests for HIV will be excluded from study inclusion.

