#### 12.3.4 Serum Pregnancy Test

Blood samples for serum pregnancy test must be obtained for analysis in the study's central laboratory at Screening Visit 1 for female subjects of childbearing potential. However, eligibility for inclusion may be determined with recently performed, reliable, serum pregnancy test obtained at a local, non-study laboratory or a reliable serum pregnancy test to be obtained at a local non-study laboratory. In all cases the results of the serum pregnancy test must be available and documented by Visit 2. Subjects with positive serum pregnancy tests will be excluded from study inclusion

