#### 13.9.1 Immune Modulating Regimen

All subjects will receive a peri-treatment systemic oral immune modulating regimen for the prevention or diminution of ocular inflammation related to IVT injection of GS010. The immune modulating regimen will consist of oral corticosteroid starting 2-days prior to the initial treatment administration to any eye of the subject and will be completed after a 28-day immune modulating regimen. The following regimen will be administered:

- Immune modulating agent: corticosteroid
- Route of administration: per os (p.o.; i.e. orally)
- Administration regimen:

- 40 milligrams (mg) daily for 1 week, starting two days prior to treatment administration to any eye of the subject, then
- 30 mg daily for 1 week, then
- 20 mg daily for 1 week, then
- 10 mg daily for one week → then stop

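### The oral corticosteroid must start one day before Visit 2, but genotype, HIV, serum pregnancy and laboratory results are not due until Visit 2

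*Protocol*

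**What the plan says.** **Start of the steroid.** Protocol 11.1.1 states: "The immune modulating regimen will be initiated after conducting the Screening Visit (Visit 1) and prior to conducting the Inclusion Visit (Visit 2"). Section 13.9.1 gives the exact day, "starting 2-days prior to the initial treatment administration to any eye of the subject", at 40 mg daily for the first week. Footnote 6 to the schedule of events (9.2) repeats the two-day rule.

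**First injection.** Protocol 11.1.3: "The initial treatment administration must be conducted the day following the Inclusion Visit (Visit 2"). Rule 3 in 9.1 says the same.

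**When eligibility results are due.**
- Genotype (12.3.1): "must be documented by the completion of Inclusion Visit 2 and prior to randomization".
- Haematology and chemistry (12.3.2): "results must be available by Inclusion Visit 2 to be considered for eligibility for inclusion".
- HIV (12.3.3): "In all cases the results of the HIV test must be available and documented by Visit 2".
- Serum pregnancy (12.3.4): "In all cases the results of the serum pregnancy test must be available and documented by Visit 2".

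**When they are reviewed for eligibility.** Section 11.1.2 lists "Review of laboratory assessment results obtained at Visit 1" as a Visit 2 procedure.

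**The concern.** The stated purpose of the regimen is to prevent or reduce ocular inflammation from the GS010 injection. A subject excluded at Visit 2 never has that injection, so any dose already taken serves no stated purpose for that subject.

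Genotype, HIV and pregnancy status are inclusion criteria (10.2.3). Laboratory abnormalities that make participation unsafe are an exclusion criterion (10.2.4). These can be known from the Visit 1 blood draw or from earlier or local results. The protocol nevertheless sets their deadline one day after a systemic steroid has begun. What is at stake is a small and largely avoidable exposure. The primary comparison involves randomised subjects only and is not touched.

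**Working it through.** **Inputs**
- First dose: 2 days before the first injection (13.9.1; 9.2 footnote 6).
- First injection: Visit 2 + 1 day (9.1 rule 3; 11.1.3).
- Study days for the same-day and two-day options: Table 1 in 9.1.
- Visit 1: Day -28 to Day -7 (11.1.1).
- Dose: 40, 30, 20 and 10 mg daily for one week each (13.9.1).
- Screening plan: 23% failure, about 117 screened for about 90 treated (10.1).

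**1. The plan's screening figure.** 90 / (1 - 0.23) = 116.9, or 117. It reproduces.

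**2. First dose relative to Visit 2.** First dose = (Visit 2 + 1) - 2 = Visit 2 - 1 day.

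| | Same-day option | Two-day option |
|---|---|---|
| First dose | Day -2 | Day -3 |
| Visit 2 | Day -1 | Day -2 |
| First injection | Day 0 | Day -1 |
| First dose to Visit 2 | 1 day | 1 day |
| Visit 1 to Visit 2 | 6 to 27 days | 5 to 26 days |
| Visit 1 to first dose | 5 to 26 days | 4 to 25 days |

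The start one day before Visit 2 is required, not merely allowed. What the text leaves open is whether results may still be pending on that day.

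**3. Does any other text make the dose wait?**
- 9.2 footnote 11 and 11.1.1 require the immune-response and bio-dissemination samples to be drawn before the regimen starts. That governs sample collection and does not require any eligibility result.
- 13.8 restricts dispensing to subjects meeting all criteria, but only for GS010 and placebo.
- 14.6 excludes a subject whose pregnancy is confirmed before the study product is given. It does not mention the steroid.
- 12.3.10 asks for timely review of results as they arrive and sets no deadline before dosing.
- 13.9.1 gives dose and duration with no precondition.

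None of these closes the gap.

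**4. Exposure by the Visit 2 decision.** One dose the day before, and possibly one on the day of Visit 2: 1 to 2 x 40 mg = 40 to 80 mg. Full course: 7 x (40 + 30 + 20 + 10) = 700 mg. Share: 40/700 = 5.7% to 80/700 = 11.4%.

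**5. Number of subjects.** Planned screen failures: 117 - 90 = 27. This is a ceiling and not an estimate. Section 10.1 does not divide failures between Visit 1 and Visit 2, or by cause.

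**The case against.** The case against rests on five points.

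- **The sequence is deliberate.** A two-day lead-in followed by baseline vision testing the day before injection is a reasonable design. This stands, and the point does not ask to change it.
- **Results will often be in hand.** There are at least 4 to 5 days between Visit 1 and the first dose, and prior or local results are accepted. Vision loss due to ND4 LHON is already a selection criterion at Visit 1 (10.2.1, criterion 2), and inability to tolerate the regimen is a non-selection criterion (10.2.2, criterion 17). This lowers the likely frequency, especially for genotype. It does not remove the gap, because 12.3.1 still allows genotype to be documented as late as the end of Visit 2, and criterion 17 is judged at the visit where the blood is drawn.
- **Safety follow-up exists.** Adverse events are captured from consent (14) and followed to resolution or the last planned visit (14.5), and pregnancies are followed to their outcome (14.6). This stands and makes an extra follow-up contact largely redundant. It acts after exposure and does not prevent it.
- **A wait has a cost.** A subject at Day -28, or at 365 days of vision loss, cannot be delayed by even one day without losing eligibility or breaching the window. This stands and must be weighed.
- **Controls may sit elsewhere.** The IRS User Guide, the study manuals or the consent form may already hold the first dose back. None was available, so the point is confined to the protocol text.

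A reader might infer from the 23% failure rate that about 27 subjects would take an unnecessary steroid. The documents do not support that. A subject who fails at Visit 1 is not selected and should not start the regimen. Many Visit 2 failures would rest on findings made at that visit, such as acuity below hand motion, incomplete idebenone washout, active ocular infection or substance abuse. Earlier laboratory results would not prevent those.

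**Conclusion.** The point holds as a minor subject-safety matter. The protocol requires the first steroid dose one day before Visit 2, while the four types of eligibility result are due at Visit 2 or by its completion. A compliant site may therefore give 40 to 80 mg to a subject whom those results then exclude. This needs both a late result and a disqualifying one. The number of such subjects is unknown, may be zero, and should be well below 27. The number the fix would spare cannot be estimated from the documents.

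A reader might also infer that ineligible subjects could be randomised or injected, or that the efficacy analysis is at risk. Neither follows. Genotype must be documented before randomisation (12.3.1), and GS010 and placebo go only to subjects meeting all criteria (13.8). The primary analysis, alpha and power are unaffected.

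The conclusion assumes that sites follow the stated timing and that no unseen manual imposes an earlier check.

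**What to change.** **Change.** In 11.1.1 and 13.9.1, require HIV, serum pregnancy (where applicable), haematology/chemistry and genotype results to be documented and reviewed before the first dose of the regimen. Prior or local-laboratory results would remain acceptable. In 11.1.2, state that a subject who has started the regimen and fails at Visit 2 stops it. Dose, duration and visit windows stay as they are.

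**Cost.** A sentence in each of the three sections and a site checklist item. With Visit 1 at Day -7, the time for results falls from 6 to 5 days (same-day option) or from 5 to 4 days (two-day option). Occasionally the first dose, Visit 2 and injection will move together by about one day within the existing windows. For a subject with no slack, at Day -28 or at 365 days of vision loss, sites should rely on local or prior results so that entry is not lost.

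Protocol 9.1.2 places the last Year 2 visit in Q3 2021 and the current SAP is dated 10 October 2024, so treatment in this trial should be over. The practical use is in any later protocol that reuses this screening and steroid text.
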